9.7.3 CLASSIFICATION OF AN ADVERSE EVENT

9.7.3.1 SEVERITY OF EVENT

For adverse events (AEs) not included in the protocol defined grading system, the Common Terminology Criteria for Adverse Events (CTCAE) Version 5.0 guidelines will be used to describe severity.

- **Grade 1 Mild** - asymptomatic or mild symptoms; clinical or diagnostic observations only; intervention not indicated.
- **Grade 2 Moderate** - minimal, local or noninvasive intervention indicated; limiting age-appropriate instrumental activities of daily living (ADL).
- **Grade 3 Severe** - medically significant but not immediately life-threatening; hospitalization or prolongation of hospitalization indicated; disabling; limiting self care ADL.
- **Grade 4 Life-threatening** - urgent intervention indicated.
- **Grade 5 Death**

9.7.3.2 RELATIONSHIP TO STUDY INTERVENTION

All adverse events (AEs) will have their relationship to study intervention assessed by a designated blinded study physician at each site. Additional AE adjudication will be provided by the Medical Monitor ([name]) who will review all AEs in an unblinded fashion as is currently recommended by the FDA for SAEs (Guidance for Industry and Investigators Safety: Reporting Requirements for INDs and BA/BE Studies (Section VI.C); December 2012). The Medical Monitors at the DCC will work collaboratively with the reporting investigator to determine if a serious adverse event has a reasonable possibility of having been caused by the study drug or procedure.

The degree of certainty about causality will be graded using the categories below. In a clinical trial, the study product must always be suspect.

- **Definitely Related** – There is clear evidence to suggest a causal relationship, and other possible contributing factors can be ruled out.
- **Probably Related** – There is evidence to suggest a causal relationship, and the influence of other factors is unlikely.
- **Possibly Related** – There is some evidence to suggest a causal relationship (e.g., the event occurred within a reasonable time after administration of the trial medication). However, other factors may have contributed to the event (e.g., the participant's clinical condition, other concomitant events).
- **Probably not related** – A clinical event, including an abnormal laboratory test result, whose temporal relationship to study intervention administration makes a causal relationship improbable (e.g., the event did not occur within a reasonable time after administration of the study intervention) and in which other drugs or chemicals or underlying disease provides plausible explanations (e.g., the participant's clinical condition, other concomitant treatments).
- **Not Related** – The AE is completely independent of study intervention administration, and/or evidence exists that the event is definitely related to another etiology. There must be an alternative, definitive etiology documented by the clinician.

Administration related adverse events, as outlined in **Section 9.7.4** of the protocol will always be considered suspected adverse reactions if they occur within 48 hours of study drug exposure.

9.7.3.3 EXPECTEDNESS

The designated blinded study physician at each site and the Medical Monitors will be responsible for determining whether an AE is expected or unexpected. An AE will be considered unexpected if the nature, severity, or frequency of the event is not consistent with the risk information previously described for the study product as described in the Investigator's Brochure.

9.7.4 TIME PERIOD AND FREQUENCY FOR EVENT ASSESSMENT AND FOLLOW-UP

Designated blinded study physicians will determine daily if any clinical adverse events occur during the period from enrollment to study day 7. Adverse event collection begins after the patient or surrogate has signed informed consent and has received study drug or undergone study procedures. If a patient experiences an adverse event after consent, but prior to receiving study product, the event will NOT be collected unless the investigator feels the event may have been caused by a protocol procedure. The designated blinded study physician will evaluate any changes in laboratory values and physical signs and will determine if these changes are clinically important. All clinically important adverse events will be recorded in the case report form regardless of attribution to study product. After study day 7, adverse events are not required to be reported unless the investigator feels the events were related to either study product or a protocol procedure.

All AEs including local and systemic reactions not meeting the criteria for SAEs will be captured on the appropriate case report form (CRF). Information to be collected includes event description, time of onset, clinician's assessment of severity, relationship to study product (assessed only by those with the training and authority to make a diagnosis), and time of resolution/stabilization of the event. All AEs occurring while on study must be documented appropriately regardless of relationship. All AEs will be followed to adequate resolution. Any medical condition that is present at the time that the participant is screened will be considered as baseline and not reported as an AE. However, if the pre-existing medical condition deteriorates at any time between the first study product administration and study day 7, it will be recorded as an AE. Organ failures related to ARDS or the patient's underlying condition that are systematically captured by the protocol should not be reported as adverse events ***unless they are considered to be study related.***

Changes in the severity of an AE will be documented to allow an assessment of the duration of the event at each level of severity to be performed.

AEs will be followed for outcome information until resolution or stabilization or until 28 days (or hospital discharge whichever occurs first) after enrollment.

For this trial, a subset of adverse events will be considered to be "administration related adverse events". These "administration related adverse events" will by definition be considered suspected adverse reactions, as outlined in **Section 7.1.8**. These events are:

- New onset atrial or ventricular arrhythmias requiring DC cardioversion within 48 hours of study drug administration
- Myocardial infarction within 48 hours of study drug administration
- CVA within 48 hours of study drug administration
- Increase in O₂ requirements defined as: an increase in FiO₂ of ≥ 0.2 **AND** increase in PEEP ≥ 5 cm H₂O within 6 hours of study drug administration
- Increase in lactate by 2 mmol/L within 6 hours of study drug administration
- Increase in any protocol specified measurement of COHb $\geq 10\%$

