1.3 SCHEMA

TIME-EVENTS SCHEDULE

Measurement/Event	Baseline	Day 1	Day 2	Day 3	Day 4	Day 5	Day 7	Day 14	Day 28	Day 60	6M
Demographic/Admission Data/Medical Hx	X										
Etiology of ARDS	X										
Physical Exam	X										
Height/Body weight	X										
Time on ventilator prior to enrollment	X										
Pregnancy test	X										
Vital Signs (HR, SBP, DBP, MAP, T) ^B	X	X	X	X	X	X	X				
Central venous pressure ^B	A	A	A	A	A	A					
Electrocardiogram (EKG)	X	X	X	X	A	A	X				
Ventilator parameters ^{B, C}	X	X	X	X	X	X	X	X			
Chest X-ray (CXR) review ^D	X	A ^D	A ^D	A ^D	A ^D	A ^D	X				
Lung Injury Score (LIS)	X	X	X	X	X	X	X				
APACHE II Score	X										
SOFA Score ^E	X	X	X	X	X	X	X	X	X		
Glasgow Coma Score (GCS)	X	X	X	X	X	X	X	X	X ^F		
Richmond Agitation Sedation Scale (RASS)	X	X	X	X	X	X	X				
Arterial Blood Gas (ABG)	X										
ABG; Venous Blood Gas if ABG not available ^C		X	X	X	A	A	X	A			
SpO2	X	X	X	X	X	X	X	A			
ScvO2	A	A	A	A	A	A					
Complete blood count (CBC) ^C	X	X	X	X	A	A	A	A	A		
Basic metabolic panel ^C	X	A	A	A	A	A	A	A	A		
PT/PTT/INR ^C	A	A	A	A	A	A	A				
Serum CK, AST, ALT, Albumin, Total Protein ^C	A	A	A	A	A	A	A				
Bilirubin ^C	X	X	X	X	X	X	X	X	X		
Lactate ^C	X	X	X	X	A	A	A				
CO Administration Parameters / Treatment		X ^G	X ^G	X ^G							
Pulmonary Dead Space (Vd/Vt) Measurement		X	X	X			X				
COHb and SpCO		X ^G	X ^G	X ^G							
Vasopressors and inotropes ^B	X	X	X	X	X	X	X	X			
Fluid intake and output ^B	X	X	X	X	X	X					
Renal replacement therapy status	X	X	X	X	X	X	X	X			
Concomitant medications	X	X	X	X	X	X	X				
Adverse event monitoring ^H		X	X	X	X	X	X ^H				
Plasma isolation		X	X	X		X					

Measurement/Event	Baseline	Day 1	Day 2	Day 3	Day 4	Day 5	Day 7	Day 14	Day 28	Day 60	6M
RNA banking		X	X	X		X					
DNA banking – Cell pellet isolation		X	X	X		X					
Primary cell (PBMC) isolation		X				X					
Urine sample collection		X	X	X		X					
Discarded BAL and plasma ^I	A	A	A	A	A	A	A				
Microbiological results ^J	A	A	A	A	A	A	A	A	A		
Vital Status									X	X	X
Discharge Status									X	X	
Ventilator Status									X	X	
Vasopressor Status									X	X	
Neurocognitive Outcomes-MoCA-BLIND, Hayling											X

X - Required

A - When available

B - Data gathered at times indicated or until patient achieves 48 hours of unassisted breathing, whichever is sooner. Data will be obtained pre- and post-treatment on study drug administration days.

C - Measure during reference period (03:00-10:00), obtain at time closest to study drug administration if applicable

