4.3 PRIMARY SAFETY ENDPOINT

The primary safety endpoint is to evaluate the safety of inhaled CO, by determining COHb levels and the incidence of pre-specified administration-related adverse events.

- Safety of inhaled CO, defined by the incidence of pre-specified administration-related AEs (as defined below) and spontaneously reported AEs through study day 7.
 - Acute MI within 48 hours of study drug administration
 - Acute cerebrovascular accident (CVA) within 48 hours of study drug administration
 - New onset atrial or ventricular arrhythmia requiring DC cardioversion within 48 hours of study drug administration
 - Increased oxygenation requirements defined as: an increase in FiO_2 of ≥ 0.2 **AND** increase in $\text{PEEP} \geq 5$ cm H_2O within 6 hours of study drug administration
 - Increase in COHb $\geq 10\%$
 - Increase in lactate by ≥ 2 mmol/L within 6 hours of study drug administration

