7.1.4 CO MONITORING

The study drug concentration will be monitored continuously with the COventDS built-in analyzer to assure that the accurate dose is delivered. A physician investigator will assess subjects prior to daily iCO treatment. Subjects will have blood drawn daily for measurement of COHb and lactate prior to study drug administration. If COHb \geq 3% (assessed by unblinded physician) or lactate \geq 4 mmol/L, the study drug will be held and the subject will be reassessed for treatment the following day. An electrocardiogram (EKG) will also be performed daily prior to study drug administration to evaluate for cardiac exclusion criteria. Blood COHb levels will be measured with an IL GEM Premier Co-oximeter and SpCO measured with a noninvasive pulse oximeter (Masimo Radical-7).

Blood (arterial or venous) will also be drawn at 20, 60, 75, 90, and 180 minutes for safety monitoring of COHb levels. If an arterial line is not available, venous blood will be used for COHb monitoring as we⁴⁸ and others¹⁴³⁻¹⁴⁵ have shown that venous levels are as accurate and reliable as arterial measurements. Blood (arterial or venous) will also be drawn for blood gas analysis (using the local clinical lab) at 90 minutes or at the completion of treatment, if discontinued sooner than 90 minutes. If arterial blood is not available and venous blood gas is used, PaO₂/FiO₂ will be estimated using the formula $SpO_2/FiO_2 = 64 + 0.84 \times PaO_2/FiO_2$, as long as SpO₂ \leq 97% and subject remains intubated as described in the Statistical Analysis Plan.

The unblinded physician will review and adjudicate COHb measurements and communicate any study drug treatment holds to the administering study staff. COHb levels will be entered into the electronic case report forms (eCRFs) in a separate limited-access project in StudyTRAX by the unblinded RT or physician. The study drug will be administered for up to 90 minutes daily for up to 3 days following randomization or until discontinuation of mechanical ventilation, whichever occurs first.

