9.5 STUDY DRUG ADMINISTRATION ASSESSMENTS (DAY 1-3)

The following assessments will be done on Days 1 – 3 prior to study drug administration. **No treatment will be started before these assessments are performed and the pre-treatment checklist is completed by the study investigator**

Calibration of IL GEM Premier Co-oximeter and COventDS: Calibration will be performed according to device manuals and SOP. Documentation of calibration will be kept in study files.

COHb Level: The baseline COHb level will be drawn and assessed by an unblinded physician investigator, just prior (less than 15 minutes) to starting the study drug administration. COHb will be measured by study investigators using an IL GEM Premier Co-oximeter at the patient's bedside. These results are obtained within less than 5 minutes. The study drug will not be started until this result is obtained and reviewed for a potential study hold. All COHb level result printouts should be filed in the unblinded subject file.

Lactate Level: Lactate level will be measured and assessed daily by the local laboratory at each center prior to study drug administration. The study drug will not be started until this result is obtained and reviewed by the study physician investigator for a potential study hold.

Hemoglobin Level: Hemoglobin will be measured and assessed daily prior to study drug administration. The hemoglobin level will be measured by the local laboratory at each center. The study drug will not be started until this result is obtained and reviewed by the study physician investigator for a potential study hold.

EKG: A 12 lead EKG will be obtained and reviewed daily by the study staff physician prior to study drug administration to evaluate for cardiac exclusion criteria ie. acute MI, ACS, or unstable atrial or ventricular arrhythmia. The study drug will not be started until the EKG is obtained and reviewed by the study physician investigator for a potential study hold. The EKG will also be officially read locally at each site.

Review Ventilator Parameters: The study staff will record ventilator parameters prior to starting study drug administration.

Calculate Deadspace (Vd/Vt): Dead space fraction will be measured daily by the administering RT or physician prior to study drug administration using a NICO or NM3 monitor (Respironics) and the PCO₂ obtained from an arterial or venous blood gas.

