9.5.2 STUDY DRUG ADMINISTRATION AND MONITORING

The study drug will be administered for up to 90 minutes daily for up to 3 days following randomization or until discontinuation of mechanical ventilation, whichever occurs first according to **Section 7.1.9**. See **Sections 7.1.6, 7.1.7, and 7.1.8** for information about study drug hold, interruption, and permanent discontinuation criteria.

Monitoring during Study Drug Administration:

Subjects will be monitored with continuous pulse oximetry, cardiac monitoring, and either intermittent (at least every 15 minutes) or continuous blood pressure monitoring (if an arterial line is in place) throughout the course of the 90 minute study drug treatment.

SpCO and SpO₂ will be monitored continuously using a Masimo Rad-7 non-invasive pulse oximeter, and recorded at the time points specified below. COHb levels will be measured using an IL GEM Premier Co-oximeter and recorded at the time points specified below. Arterial or venous blood will be drawn for blood gas analysis prior to treatment and at the completion of study drug administration (90 min or earlier if discontinued prior to 90 min). If study drug treatment is discontinued prior to 90 min, all of the scheduled 90-minute measurements will be made and recorded at the time of study drug discontinuation.

Ambient CO levels will be monitored continuously using a Dräger Pac 7000 CO detector, and recorded at the time points specified below.

	ABG or VBG (pH, PCO ₂ , PO ₂)	FiO ₂	COHb level (IL GEM Premier co-oximeter)	CFK look-up table (Appendix B or StudyTRAX)	SpCO (Masimo Rad-7)	SpO ₂ (Masimo Rad-7)	Ambient CO Level (Dräger Pac CO detector)
Pre-treatment	X	X	X		X	X	X
20 min			X	X	X	X	X
60 min			X		X	X	X
75 min			X		X	X	X
90 min*	X	X	X		X	X	X
180 min			X		X	X	X

*90 min or upon completion of study product if discontinued sooner than 90 min.

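### A lactate rise within 6 hours of dosing is a primary safety component, but no lactate is required inside that window after any dose

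*Combined protocol and SAP*

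**What the plan says.** Section 4.3, repeated in 10.1, sets the primary safety endpoint as "Safety of inhaled CO, defined by the incidence of pre-specified administration-related AEs", together with spontaneously reported events through Day 7. It lists six components. The last is "Increase in lactate by ≥ 2 mmol/L within 6 hours of study drug administration". The same event is a criterion for permanent discontinuation in 7.1.8. In 9.7.4 it is an administration-related adverse event, and so a suspected adverse reaction by definition, worded there as "Increase in lactate by 2 mmol/L within 6 hours of study drug administration".

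On when lactate is taken, 7.1.4 says: "Subjects will have blood drawn daily for measurement of COHb and lactate prior to study drug administration". Section 9.5 says: "Lactate level will be measured and assessed daily by the local laboratory at each center prior to study drug administration". Section 7.1.6 uses the same pre-dose value for the daily hold. In the Time-Events Schedule the lactate row carries footnote C: "Measure during reference period (03:00-10:00), obtain at time closest to study drug administration if applicable". It does not carry footnote B, which says: "Data will be obtained pre- and post-treatment on study drug administration days".

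After dosing starts, 7.1.4 and 9.5.2 require COHb at 20, 60, 75, 90 and 180 minutes. Section 9.5.2 adds: "Arterial or venous blood will be drawn for blood gas analysis prior to treatment and at the completion of study drug administration". Its table heads that blood gas column with pH, PCO2 and PO2; 9.1 and 9.5 add base excess or deficit to the values recorded. Lactate is in neither list. On Days 4, 5 and 7 the schedule and 9.6 take lactate only when available.

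**The concern.** A rise needs two values: one before the dose and one inside the 6 hours after it. The plan guarantees the first and not the second. This component is therefore seen only if someone obtains a lactate that the protocol does not ask for.

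Three things are at stake. First, the count for this component cannot be interpreted: a patient with no recorded rise may have had none, or may not have been tested. Second, the same unmeasured event is meant to operate the discontinuation criterion in 7.1.8 and the 7-day report to the DSMB in 9.7.6. Third, the risk sections (3.3.1, 3.3.3) name COHb and lactate together as what will be watched during CO exposure, so a reader of the results would take a low lactate count as evidence from systematic monitoring.

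**Working it through.** **Step 1: required measurement of the comparable components.** Three of the six components rest on a laboratory or ventilator value.

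- COHb of 10% or more: five required values after dosing starts (7.1.4, 9.5.2).
- FiO2 and PEEP increase within 6 hours: ventilator parameters carry footnote B, so they are collected before and after treatment.
- Lactate rise within 6 hours: one required value, before dosing (7.1.4, 7.1.6, 9.5; footnote C). Required values after dosing: none.

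Footnote C's phrase about the time closest to administration does not rescue the post-dose value. Section 9.5 says the drug is not started until the lactate result is available, so the required sample precedes the dose.

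**Step 2: could the next scheduled lactate fall inside the window?** The next required lactate is the following day's, in a reference period that opens at 03:00. The documents give no clock time for dosing, so I assume a range. Hours from start of dosing to the opening of that period = 27 - start hour.

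- Start 08:00: 27 - 8 = 19 hours.
- Start 14:00: 27 - 14 = 13 hours.
- Start 20:00: 27 - 20 = 7 hours.

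All exceed 6 hours from the start of dosing. If the 6 hours run from the end of a 90-minute dose, the limit is 7.5 hours after the start, and any start before 19:30 (27 - 7.5 = 19.5) still falls outside. Only late-evening dosing could bring the next sample into the window, and no text plans for that. After the Day 3 dose there is no next required lactate at all.

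**Step 3: extent.** 32 patients x 3 doses = 96 dosing windows, each with no required post-dose lactate. This is a ceiling, because some doses will be held or not given.

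**Step 4: the plan's own detection figure.** Table 6 gives the chance of at least one event on iCO, P = 1 - (1 - p)^n, labelled n = 16. At p = 0.10 it prints 0.77.

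- n = 16: 1 - 0.90^16 = 0.815. This does not match.
- n = 14: 1 - 0.90^14 = 0.771. This matches, and n = 14 reproduces all seven rows of the table. It fits 16 less about 10% loss (16 x 0.9 = 14.4).

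**Step 5: illustration of incomplete capture.** Table 6 assumes every event is seen. If only a share q is measured, P = 1 - (1 - pq)^n. The documents give no q; I take 0.2 to 0.5 with p = 0.10.

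- n = 16: q = 1 gives 0.815; q = 0.5 gives 1 - 0.95^16 = 0.560; q = 0.2 gives 1 - 0.98^16 = 0.276.
- n = 14: q = 1 gives 0.771; q = 0.5 gives 1 - 0.95^14 = 0.512; q = 0.2 gives 1 - 0.98^14 = 0.246.

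Both p and q are assumptions. The finding rests on Steps 1 to 3, not on these figures.

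**The case against.** The best reply is that a post-dose lactate was intended. Section 7.1.5 says about 2.5 mL is drawn during administration on each of Days 1-3, and the blood-volume table in 9.1.1 assigns 2.5 mL on each of those days to blood gas, lactate and COHb together. The volumes match, and 3.3.1 and 3.3.3 promise careful monitoring of lactate as outlined. This stands as a sign of intent and makes an internal inconsistency more likely than a deliberate choice. It does not supply the measurement. Section 7.1.5 names only COHb and blood gas as the purpose of that blood, the 9.1.1 row gives no time and could equally cover the pre-dose lactate, and no section schedules or records a post-dose value. The appendices are not in the text available to me, so I cannot say whether they add one.

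A second reply is that patients are not unwatched. The blood gas yields base excess or deficit, a local analyser may print lactate, and designated blinded physicians review laboratory changes daily (9.7.4). All true, but base excess is not the endpoint, and a lactate that is neither required nor recorded cannot be relied on for one.

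A third is that this is one component of six and that 9.7.5 plans no formal testing of adverse events. That limits the damage to one line of the safety report. A descriptive count still needs a known denominator.

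A reader might also infer that ascertainment will differ between arms, because the administering physician is unblinded and stays available for 90 minutes after dosing. The documents do not support that as a finding. The same kind of staff attend both arms, the treating ICU team is blinded (7, 7.3), and extra testing in iCO patients would raise the iCO count rather than lower it. It is a possibility of unknown direction.

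**Conclusion.** The plan as written does not measure one component of its primary safety endpoint: none of up to 96 dosing windows has a required lactate in the 6 hours that define the event. A low count would therefore overstate safety. This follows from the text and needs no assumption beyond dosing not taking place late in the evening; for the third dose it needs none.

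The size of the under-count cannot be derived from the documents. A reader might take the fall from 81% to 28-56% (n = 16), or from 77% to 25-51% (n = 14), as an estimate. It only shows what an assumed 10% rate and 20-50% capture would imply. Nor do the documents say how long after a dose the next lactate would come: the gap depends on a dosing time they do not state. And they do not show that post-dose lactate was deliberately left out, since the matching 2.5 mL volumes suggest it may have been intended.

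**What to change.** Reconcile 4.3, 7.1.5, 7.1.8, 9.1.1, 9.5.2, 9.7.4 and the Time-Events Schedule on the lactate component:

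- Require and record lactate, in both arms, on at least one post-dose draw already scheduled inside the 6-hour window. The 90-minute or end-of-dose blood gas and the 180-minute sample both qualify; the sponsor should choose the time.
- State which value the rise is measured from for the endpoint. None of the lists says so now.
- Report, by arm, how many dosing windows had a post-dose lactate, so that the count has a denominator.

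The cost is one extra analyte on an existing draw on Days 1-3, a CRF field and edits to the 9.5.2 table and the schedule. One value at 90 or 180 minutes still leaves part of the 6-hour window unsampled, and the report should say so. Because the same event is a discontinuation criterion, the endpoint and 7.1.8 passages must agree on how it is measured. No change to the threshold or to the discontinuation rule is proposed.
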